#### **5.3.2.3 Assent of Adults Unable to Consent**

Describe the process for assent of the subjects. Indicate whether assent will be required of all, some or none of the subjects. If some, indicate which subjects will be required to assent and which will not.

If assent will not be obtained from some or all subjects, provide an explanation of why not.

Describe whether assent of the subjects will be documented and the process to document assent. The IRB allows the person obtaining assent to document assent on the consent document and does not routinely require assent documents and does not routinely require subjects to sign assent documents.

Not applicable.

### **5.3.3 Subjects who are not yet adults (infants, children, teenagers)**

#### **5.3.3.1 Parental Permission**

Describe whether and how parental permission will be obtained. If permission will be obtained from individuals other than parents, describe who will be allowed to provide permission. Describe the process used to determine these individual's authority to consent to each child's general medical care.

For research conducted in the state, review "SOP: Legally Authorized Representatives, Children and Guardians (HRP-013)" to be aware of which individuals in the state meet the definition of "children". HRP-013 can be accessed by clicking the Library link in CATS IRB (<http://irb.psu.edu>).

For research conducted outside of the state, provide information that describes which persons have not attained the legal age for consent to treatments or procedures involved in the research, under the applicable law of the jurisdiction in which research will be conducted. One method of obtaining this information is to have a legal counsel or authority review your protocol along with the definition of "children" in "SOP: Legally Authorized Representatives, Children, and Guardians (HRP-013)." HRP-013 can be accessed by clicking the Library link in CATS IRB (<http://irb.psu.edu>).

Not applicable.

#### 5.3.3.2 Assent of subjects who are not yet adults

Indicate whether assent will be obtained from all, some, or none of the children. If assent will be obtained from some children, indicate which children will be required to assent. When assent of children is obtained describe whether and how it will be documented.

Not applicable.

## 6.0 HIPAA Research Authorization and/or Waiver or Alteration of Authorization

This section is about the access, use or disclosure of Protected Health Information (PHI). PHI is individually identifiable health information (i.e., health information containing one or more 18 identifiers) that is transmitted or maintained in any form or medium by a Covered Entity or its Business Associate. A Covered Entity is a health plan, a health care clearinghouse or health care provider who transmits health information in electronic form. See the "Investigator Manual (HRP-103)" for a list of the 18 identifiers. HRP-103 can be accessed by clicking the Library link in CATS IRB (<http://irb.psu.edu>).

If requesting a waiver/alteration of HIPAA authorization, complete sections 6.2 and 6.3 in addition to section 6.1. The Privacy Rule permits waivers (or alterations) of authorization if the research meets certain conditions. Include only information that will be accessed with the waiver/alteration.

### 6.1 Authorization and/or Waiver or Alteration of Authorization for the Uses and Disclosures of PHI

Check all that apply:

- Not applicable, no identifiable protected health information (PHI) is accessed, used or disclosed in this study. [Mark all parts of sections 6.2 and 6.3 as not applicable]
- Authorization will be obtained and documented as part of the consent process. [If this is the only box checked, mark sections 6.2 and 6.3 as not applicable]
- Partial waiver is requested for recruitment purposes only (Check this box if patients' medical records will be accessed to determine eligibility before consent/authorization has been obtained). [Complete all parts of sections 6.2 and 6.3]
- Full waiver is requested for entire research study (e.g., medical record review studies). [Complete all parts of sections 6.2 and 6.3]
- Alteration is requested to waive requirement for written documentation of authorization (verbal authorization will be obtained). [Complete all parts of sections 6.2 and 6.3]

## 6.2 Waiver or Alteration of Authorization for the Uses and Disclosures of PHI

### 6.2.1 Access, use or disclosure of PHI representing no more than a minimal risk to the privacy of the individual

#### 6.2.1.1 Plan to protect PHI from improper use or disclosure

Include the following statement as written – DO NOT ALTER OR DELETE unless this section is not applicable because the research does not involve a waiver of authorization. If the section is not applicable, remove the statement and indicate as not applicable.

Not applicable

#### 6.2.1.2 Plan to destroy identifiers or a justification for retaining identifiers

Describe the plan to destroy the identifiers at the earliest opportunity consistent with the conduct of the research. Include when and how identifiers will be destroyed. If identifiers will be retained, provide the legal, health or research justification for retaining the identifiers.

Not applicable

### 6.2.2 Explanation for why the research could not practicably be conducted without access to and use of PHI

Provide an explanation for why the research could not practicably be conducted without access to and use of PHI.

Not applicable

### 6.2.3 Explanation for why the research could not practicably be conducted without the waiver or alteration of authorization

Provide an explanation for why the research could not practicably be conducted without the waiver or alteration of authorization.

Not applicable

## 6.3 Waiver or alteration of authorization statements of agreement

By submitting this study for review with a waiver of authorization, you agree to the following statement – DO NOT ALTER OR DELETE unless this section is not applicable because the research does not involve a waiver or alteration of authorization. If the section is not applicable, remove the statement and indicate as not applicable.

Not applicable

## 7.0 Study Design and Procedures

### 7.1 Study Design

Describe and explain the study design.

A two-period randomized crossover trial will be conducted. Participants will be randomized to receive each treatment for 6 weeks followed by a minimum 4-week wash-out period. During the peanut treatment, participants will consume one ounce per day (28 g) of peanuts as an evening snack. The control treatments will be an isocaloric high carbohydrate snack (crackers + spread) consumed after the evening meal. The peanuts and control foods will be provided to the participants every two weeks during the treatment periods; these foods will be purchased from one of the local supermarkets. Participants will be given instructions about when to consume the foods.

Fasting blood glucose, fructosamine, insulin, weight, lipids and lipoproteins, central and peripheral blood pressure and arterial stiffness will be measured at the beginning and the end of each treatment period. Fecal samples will be provided at the beginning and the end of each treatment period for assessment of the microbiome. A 24-hour dietary recall will be completed at the beginning and end of each diet to determine how consuming the evening snack influences overall dietary intake (including calorie and macronutrient intake and overall diet quality).

## 7.2 Study Procedures

Provide a description of all research procedures being performed and when they are being performed (broken out by visit, if applicable), including procedures being performed to monitor subjects for safety or minimize risks. Include any long-term follow-up procedures and data collection, if applicable.

Describe where or how you will be obtaining information about subjects (e.g., medical records, school records, surveys, interview questions, focus group topics, audio or video recordings, data collection forms, and collection of specimens through invasive or non-invasive procedures to include the amount to be collected and how often). Add any data collection instruments that will be seen by subjects to your study in CATS IRB (<http://irb.psu.edu>) in the “Supporting Documents” page.

### 7.2.1 EXAMPLE: Visit 1 or Day 1 or Pre-test, etc. (format accordingly)

Provide a description as defined above and format accordingly.

Screening: The clinical visit will consist of filling out forms (informed consent, medical history, personal information); measuring height and weight so that BMI can be calculated; and measuring blood pressure to determine eligibility. If blood pressure is >140/90 mmHg at screening the individual will require written approval from their Primary Care Physician prior to enrolling the study. Women of child bearing potential will provide a urine sample for a pregnancy test. If after these measurements, it is determined that the subject is still eligible, a blood sample will be taken and a complete blood count, including liver and kidney function and a blood lipid panel will be performed (approximately 19 mls of blood or ~1.25 tablespoon will be taken). If the initial blood draw is unsuccessful it may need to be repeated, with permission from the participant. In addition, if a potential participant takes thyroid medicine they must provide a current (within 6 months) lab test. If they do not have one, an extra 3.5 ml (0.2 Tbsp) of blood will be taken to conduct a thyroid test. If all eligibility criteria are met, participants will be scheduled for their baseline measurements. Baseline visits typically occur within 1-2 weeks following the screening appointment.

### 7.2.2 EXAMPLE: Visit 2 or Day 2 or Post-test, etc. (format accordingly)

Provide a description as defined above and format accordingly.

Baseline and endpoint visits (8 total):

At the beginning and end of each diet period, two fasting blood samples will be collected (separated by at least 24 hours) for analysis of biochemical endpoints. Body weight will be taken

and vascular health assessments using the SphygmoCor will be performed at the beginning and end of each diet period. Participants will also complete a fecal collection at the beginning and end of each treatment period. Participants will complete a 24-hour dietary recall at the beginning and end of each treatment period.

**Plasma/serum analysis:** In addition to the blood taken at screening, 12 hour fasting blood samples also will be taken on two consecutive days at the beginning and end of each treatment period for a total of 8 times. Approximately 60 ml (about 4 Tbsp) will be collected across the two visits (30 ml per day). A typical American Red Cross blood donation is 1 pint (500 ml). Blood may be analyzed for the following: blood lipids and lipoproteins, glucose and insulin, and Fructosamine.

**Central Blood Pressure and Augmentation Index:** Following a 5-minute rest period, brachial artery systolic and diastolic blood pressure will be measured in the left arm using an automated blood pressure cuff. The cuff will reinflate and obtain a pulse wave form. Central blood pressure and wave reflection characteristics (augmentation index) will then be derived from the pressure waveforms using a validated transfer function with a SphygmoCor System (AtCor Medical, Sydney, Australia). This test will be performed in triplicate.

**Pulse Wave Velocity:** Arterial stiffness will be assessed by calculating the pulse wave velocity (PWV) between the carotid and femoral arteries while in the supine position. A cuff will be placed on the participant's thigh. The cuff will inflate during the test to record the pulse waveform in the femoral artery. A simultaneous measurement of the carotid artery pressure waveform will be obtained by an applanation tonometry sensor manually held in place above the carotid artery. PWV will subsequently be calculated by dividing the linear distance between the carotid and femoral sites by the transit time using the SphygmoCor system (AtCor Medical, Sydney Australia). This measurement will be performed in triplicate.

**Fecal collection:** At the beginning and end of each treatment period, participants will be asked to collect a stool sample (~50 g). They will be provided with a stool sample kit and detailed instructions for collection of a clean sample.

**Dietary intake:** The 24-hour recall will be administered through the Automated Self Administered 24-Hour (ASA24®) Dietary Assessment Tool. This is an online system where participants will provide information about all foods, beverages and supplements consumed during the previous day. No identifying information is uploaded to this system, participant ID numbers are used to identify the 24-hour records. Participants will have the option of completing the 24-hour recall at home or at the visit. This system generates food group and nutrient data from the 24- hour recalls. These data will be used for calculation of diet quality.

**Daily monitoring form:** Participants will complete daily monitoring forms regarding consumption of test foods, changes in medication or health during the study. When they pick up their tests food biweekly, they will be provided with the daily monitoring forms and asked to return the completed forms the next time they pick up food.

### 7.3 Duration of Participation

Describe the duration of an individual subject's participation in the study.

Each participant will be involved in the study for approximately 16 weeks; two treatment periods each lasting 6 weeks, separated by a  $\geq$  4 week break. Participants will be expected to pick up the test foods

biweekly at the diet center on campus. At the beginning and end of each diet period, data collection (described above) will occur.

Total time for study visits, after the initial screening is approximately 6 hours. Times may vary and females will require an additional 5 minutes for a urine pregnancy test a baseline and the end of each diet period. The following is an estimate of the amount of time participants will spend in study activities:

- Screening appointment:  
Day 1: Forms, blood pressure, weight, height, blood draw – 45-60 minutes  
(pregnancy testing: females only – 5 minutes)
- Beginning of treatment period 1 and 2  
Day 1: blood draw, weight, PWA, PWV – 60 minutes  
(pregnancy testing: females only – 5 minutes)  
Day 2: blood draw – 30 minutes
- End of treatment period 1 and 2:  
Day 1: blood draw, weight, PWA, PWV – 60 minutes  
(pregnancy testing: females only – 5 minutes)  
Day 2: blood draw – 30 minutes
- Picking up food, fecal collections, and completing 24-hour diet recalls : ~ 5 hours

Total time for clinic and diet center visits from the beginning to the end of the study ~11 hours

## 8.0 Subject Numbers and Statistical Plan

### 8.1 Number of Subjects

Indicate the total number of subjects to be accrued.

If applicable, distinguish between the number of subjects who are expected to be enrolled and screened, and the number of subjects needed to complete the research procedures (i.e., numbers of subjects excluding screen failures.)

Approximately 135 subjects will complete the screening process for this study; of those we anticipate 59 subjects to be eligible A total of 45 participants will complete the study. To achieve this, we will likely need to randomize 59 subjects assuming a 30% drop out rate.

### 8.2 Sample size determination

If applicable, provide a justification of the sample size outlined in section 8.1 – to include reflections on, or calculations of, the power of the study.

To provide 80% power ( $p<0.05$ ) to detect a minimum 10 mg/dL difference in fasting glucose between the treatments, 45 participants are required (standard deviation of 23.4mg/dL). To account for a 30% drop-out rate, 59 subjects will be randomized. Completion of 45 subjects will also provide 80% power ( $p<0.05$ ) to detect a minimum 11 mg/dL (standard deviation 25.9 mg/dL) difference between the treatment in LDL-cholesterol, and a 4.5 mmHg difference in systolic blood pressure (standard deviation 11 mmHg).

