### 3.3.2 Follow-up for withdrawn subjects

Describe when and how to withdraw subjects from the study; the type and timing of the data to be collected for withdrawal of subjects; whether and how subjects are to be replaced; the follow-up for subjects withdrawn from investigational treatment.

No safety concerns; no reason for follow-up. If consent is withdrawn no data from the participant will be used. Otherwise, if consent is not withdrawn, data from individuals who withdraw from the study may be used in an intent-to-treat analysis but another individual will be enrolled to ensure that an adequate sample size (with complete data) is reached.

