### 4.2 Recruitment process

Describe how, where and when potential subjects will be recruited (e.g., approaching or providing information to potential subjects for participation in this research study).

Public advertisements (flyers/posters/ newspaper ads/circulars/ websites and social media/ radio) in the local community (State College/ University Park area) will be used to recruit people. These ads will be run periodically depending on recruitment. When an individual responds to an ad, study staff will contact the individual using the contact details provided.

A letter to local businesses or organization may be utilized requesting they share study details with their members/employees if permitted.

All of these methods of recruitment will be used until the target sample size is reached.

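### The drop-out allowance is miscalculated: 59 is 45 × 1.30, but losing 30% of those randomised requires 45/0.70, or 65, so the accrual forecast is 5 to 6 low

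*Combined protocol and SAP*

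**What the plan says.** Section 8.2 (Sample size determination) derives the number of completers from fasting glucose: "45 participants are required (standard deviation of 23.4mg/dL"). It then allows for losses: "To account for a 30% drop-out rate, 59 subjects will be randomized".

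Section 8.1 (Number of Subjects) repeats the figures. The completer target is "A total of 45 participants will complete the study", and to reach it "we will likely need to randomize 59 subjects assuming a 30% drop out rate". The screening forecast is "Approximately 135 subjects will complete the screening process for this study; of those we anticipate 59 subjects to be eligible".

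Two other sections bear on how the numbers operate. Section 3.3.2 says of participants who leave without withdrawing consent that "data from individuals who withdraw from the study may be used in an intent-to-treat analysis", but that "another individual will be enrolled to ensure that an adequate sample size (with complete data) is reached". Section 4.2 says of the recruitment channels: "All of these methods of recruitment will be used until the target sample size is reached".

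**The concern.** A drop-out rate is ordinarily a share of those randomised. Allowing for it means dividing the completer target by the proportion retained, not multiplying it by one plus the rate. The 59 matches the multiplication, so the allowance falls short of the loss that the plan itself assumes.

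Two things could be at stake. If 59 worked as a cap, the trial would finish with fewer than 45 completers and less than the intended 80% power. If 45 completers is the real target, power is kept, but the numbers to be randomised and screened are understated. Section 8.1 is where the IRB is told the total accrual. It also expects exactly 59 eligible people, all of them to be randomised, so the forecast contains no spare from which to make replacements.

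**Working it through.** **Inputs.** Completers required: 45 (sections 8.1 and 8.2). Drop-out: 30% (both). Randomised: 59 (both). Screened: about 135, of whom 59 eligible (section 8.1). Glucose difference 10 mg/dL, SD 23.4 mg/dL, 80% power, 0.05 level (section 8.2).

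**1. Reproducing the plan's figure.** 45 × (1 + 0.30) = 58.5, rounded up to 59. This matches exactly.

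**2. The allowance for losing 30% of those randomised.** 45 / (1 − 0.30) = 64.3, rounded up to 65. Check: 65 × 0.70 = 45.5, whereas 64 × 0.70 = 44.8 falls short. The difference from 59 is 5.3 before rounding and 6 after.

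**3. What 59 delivers.** 59 × 0.70 = 41.3 completers. The reserve above 45 is 59 − 45 = 14, against 64.3 − 45 = 19.3 needed (65 − 45 = 20 as planned). The largest drop-out at which 59 still gives 45 is 14/59 = 23.7%.

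**4. Screening.** The plan's own yield is 59/135 = 43.7%.

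| Randomised | Screened at that yield | Above 135 |
|---|---|---|
| 64.3 (expected) | 147.1 | 12.1 |
| 65 (rounded up) | 148.7 | 13.7 |

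**5. Chance variation.** Assume independent drop-outs at a true rate of 30%. If recruitment continues until 45 complete, the number randomised is 45 plus a negative binomial count of losses. Its mean is 45/0.70 = 64.3, its SD is √(45 × 0.30)/0.70 = 5.25, and its 5th to 95th percentiles are 56 to 73. For fixed numbers, the binomial probability of at least 45 completers is as follows.

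| Randomised | Drop-out | P(at least 45 complete) |
|---|---|---|
| 59 | 30% | 0.183 |
| 65 | 30% | 0.613 |
| 59 | 23.7% | 0.571 |

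So 65 makes the expected number of completers sufficient. It does not guarantee 45.

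**6. Power, only if enrolment stopped at 59 without replacement.** Section 8.2 names neither the test nor the kind of SD. A two-sided paired t-test with 23.4 mg/dL as the SD of the within-person difference gives n = 45 with power 0.801, so it reproduces the plan's number; a one-sided test gives 36 and does not. On that basis, 41 completers give power 0.761.

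**The case against.** The strongest reply is that this is only a forecast. Section 8.1 hedges both the screened and the randomised figures, section 3.3.2 provides for replacement, and section 4.2 keeps recruiting. No test, estimand or conclusion changes, the study is classed as minimal risk, and the shortfall is about 10% of an approximate figure. All of that stands, and it limits the consequence. It does not reconcile the three numbers, and section 8.2 states 59 without a hedge and without mentioning replacement.

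A second reply is that treating 45 completers as the governing target is an inference. That is fair. Section 3.3.2 does not name 45, section 4.2 does not say which number is its target, and the replacement sentence covers people who leave without withdrawing consent, with nothing said about those who withdraw it. It is the most natural reading of the three sections together, but the plan should say so.

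Third, the 18% chance for 59 looks worse alone than beside the 61% for 65. Both are given above for that reason. The screening projection also rests on a ratio of two rough forecasts, so it shows the order of magnitude only.

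The one reading that would rescue 59 is a drop-out rate expressed as a share of completers (14/45 = 31%). Nothing in the documents defines it that way.

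**Conclusion.** The error is certain and appears in both sample-size sections. With 45 completers and 30% drop-out, the number to randomise is about 65, not 59. This needs only the plan's own figures and the usual meaning of a drop-out rate.

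The consequence is moderate. On the reading that 45 completers governs, the planned power is largely protected, and what is wrong is the stated accrual: 5 to 6 too few randomised and about 12 to 14 too few screened, the latter assuming the 43.7% yield holds and every eligible person is randomised.

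The loss of power to about 76% would arise only if recruitment ended at 59, which no section states. It also assumes a complete-case paired t-test and the SD interpretation above, whereas section 8.3 plans mixed models and section 3.3.2 allows withdrawn participants' data to be used, which could reduce the loss. The point should be fixed, but it does not undermine the primary analysis.

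**What to change.** Restate sections 8.1 and 8.2 in one of two ways:

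1. Keep 30% drop-out and state about 65 eligible and randomised, from about 149 screened.
2. Keep 59 randomised and about 135 screened, and state the assumed drop-out as about 24% (14 of 59).

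The documents give no source for the 30%, and the 24% is simply the rate at which 59 works. The choice should follow whichever rate the team can support from its own experience, with the basis stated.

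In either case, cross-refer to the replacement rule in section 3.3.2, say that 45 completers is the stopping target and that the randomised and screened totals are expected numbers, and state whether participants who withdraw consent are also replaced.

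The cost is wording in two sections and a cross-reference. Option 1 raises the stated accrual by about 6 randomised and 14 screened, which replacement already implies at 30% drop-out. Option 2 changes only the stated rate.

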### 8.3 Statistical methods

Describe the statistical methods (or non-statistical methods of analysis) that will be employed.

The normality of the data will be tested before performing analyses, and transformations will be made if needed. Mixed effect models will be used to determine between-group changes over time and between group differences in mean values following the treatments. Treatment will be included as a fixed effect. Subject will be included as a random effect.

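### Section 8.2 claims 80% power for a 4.5 mmHg systolic blood pressure difference, but its printed inputs give about 77% (78% by the normal approximation)

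*Combined protocol and SAP*

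**What the plan says.** Section 8.2 (Sample size determination) makes three power statements at a significance level of 0.05.

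- **Fasting glucose (primary):** 80% power "to detect a minimum 10 mg/dL difference in fasting glucose between the treatments", for which "45 participants are required (standard deviation of 23.4mg/dL").
- **LDL-cholesterol (secondary):** "Completion of 45 subjects will also provide 80% power" "to detect a minimum 11 mg/dL (standard deviation 25.9 mg/dL) difference between the treatment in LDL-cholesterol".
- **Systolic blood pressure (secondary):** the same sentence continues "and a 4.5 mmHg difference in systolic blood pressure (standard deviation 11 mmHg").

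So one number of completers and one power are claimed for all three endpoints. The section does not name the test, say whether it is one- or two-sided, or say whether the SDs are of paired differences or of single measurements. Section 7.1 gives the design: "A two-period randomized crossover trial will be conducted". Section 8.3 gives a mixed model with treatment as a fixed effect, and adds: "Subject will be included as a random effect".

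**The concern.** With the same test, level and number of completers, power depends only on the ratio of the difference to its SD. The three printed ratios are not equal:

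- glucose: 10 / 23.4 = 0.427
- LDL: 11 / 25.9 = 0.425
- systolic pressure: 4.5 / 11 = 0.409

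The first two nearly agree and the third is clearly lower. If 45 completers only just give 80% for glucose, they cannot also give 80% for systolic pressure when the inputs are treated alike.

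Peripheral blood pressure is a listed secondary endpoint (section 1.3), and section 8.2 is the plan's only power justification. A reader judging a null blood pressure result would rely on a sensitivity somewhat better than the printed figures support.

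**Working it through.** **Inputs.** Completers n = 45; differences and SDs as printed in section 8.2; alpha 0.05 from section 8.2; paired comparison from the crossover in section 7.1. With complete pairs and treatment as the only fixed effect, the mixed model in section 8.3 is equivalent to a paired t-test. Two assumptions are needed: the test is two-sided, and each printed SD is the SD of the within-person difference.

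**Formulas.**

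- Noncentrality: λ = (difference / SD) × √n, with √45 = 6.708.
- Paired t power: probability that a noncentral t with 44 df and noncentrality λ falls outside ±2.015.
- Normal approximation: power = Φ(λ − 1.960).

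**Step 1: reproduce the plan's own sample size.** For glucose, λ = 0.4274 × 6.708 = 2.867. The paired t-test gives 80.06% at n = 45 and 79.1% at n = 44, so the smallest adequate n is 45, exactly as stated. The normal approximation gives n = ((1.960 + 0.842) × 23.4 / 10)² = 42.98, so 43. A one-sided t-test gives 36. With 45 in total or 45 per arm, an unpaired comparison gives only about 30% or 53% power. The two-sided paired t-test is therefore the reading that matches.

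**Step 2: apply the same test to all three endpoints at n = 45.**

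| Endpoint | λ | Paired t power | Normal approx. power | Difference detectable at 80% (paired t) |
|---|---|---|---|---|
| Glucose | 2.867 | 80.1% | 81.8% | 9.99 mg/dL (stated 10) |
| LDL | 2.849 | 79.6% | 81.3% | 11.06 mg/dL (stated 11) |
| Systolic pressure | 2.744 | 76.5% | 78.4% | 4.70 mmHg (stated 4.5) |

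Glucose and LDL agree with the text within rounding; systolic pressure does not. Allowing one degree of freedom for a period term (43 df) leaves it at 76.5%.

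**Step 3: what 80% would need for systolic pressure.**

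- Completers at 4.5 mmHg and SD 11: 49 by paired t; ((1.960 + 0.842) × 11 / 4.5)² = 46.9, so 47, by the normal approximation.
- Detectable difference at n = 45 and SD 11: 4.70 mmHg by paired t; (1.960 + 0.842) × 11 / 6.708 = 4.59 mmHg by the normal approximation.
- SD at n = 45 and 4.5 mmHg: at most 10.54 by paired t.

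**Step 4: could rounding explain it?** An SD printed as 11 lies between 10.5 and 11.5. If power need only print as 80% (at least 79.5%, a tolerance that LDL also needs), the largest SD that fits is 10.605 by paired t or 10.844 by the normal approximation. If 4.5 was itself rounded (true value up to 4.549), these become 10.72 and 10.96.

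**Step 5: could the SDs be of single measurements?** Then the SD of the difference is SD × √(2(1 − ρ)), where ρ is the within-person correlation. For 80% power by paired t at n = 45, ρ must be 0.499 for glucose, 0.505 for LDL and 0.541 for systolic pressure. The documents give no ρ. By paired t, systolic pressure power would be 62.1% at ρ = 0.3, 76.5% at 0.5 and 93.4% at 0.7.

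**The case against.** The strongest reply is that this is imprecise reporting, not a miscalculation. The systolic pressure SD is the only one of the three printed as a whole number; an SD of 10.5 prints as 11 and gives 80.3% by paired t. The test is inferred, mainly from one match (the glucose sample size), and by the normal approximation all three endpoints fall within 2 points of 80%. If the SDs are of single measurements, nothing obliges the correlation to be the same for every endpoint, and 0.54 for systolic pressure would close the gap. The endpoint is secondary and no decision turns on it.

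Much of this stands as a limit on the point. Rounding cannot be excluded, the method is an inference, and the consequence is small. It does not rescue the figure as printed:

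- Under the test that fits glucose, rounding works only if the SD lies between 10.5 and about 10.6, roughly the lowest tenth of the values that print as 11 (up to about 10.7 if 4.5 was rounded too).
- The normal approximation misses the plan's glucose sample size (43 against 45) and still leaves systolic pressure below 80%.
- The single-measurement reading needs a correlation that the plan never states. Glucose and LDL both landing at almost exactly 0.50 is also what paired-difference SDs would produce, since √(2(1 − 0.5)) = 1. A common 0.50 leaves systolic pressure at 76.5%.

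Each explanation requires an input that the documents do not contain.

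**Conclusion.** The point holds and is minor. As printed, 4.5 mmHg with SD 11 and 45 completers gives 76.5% power (paired t) or 78.4% (normal approximation), not 80%: a shortfall of 3.5 or 1.6 points. Put the other way, the detectable difference is understated by 0.2 or 0.1 mmHg.

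This rests on a two-sided 0.05 test and on reading the printed SDs as SDs of the paired difference, the reading that reproduces the glucose and LDL lines. Confidence is medium, because that reading is inferred and an unrounded SD or an unstated correlation could account for the gap. The planned 45 completers, the glucose justification and the LDL statement are not affected.

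**What to change.** In section 8.2, name the test and its sidedness and say what the SDs are SDs of. Then amend the systolic pressure clause in one of these ways:

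- If 11 mmHg is the SD of the paired difference, state 80% power for about 4.7 mmHg, or about 77% power for 4.5 mmHg.
- If a smaller unrounded SD was used (about 10.6 or less with the t-test), print it to one decimal, as for glucose and LDL, and keep the 80%.
- If the SDs are of single measurements, print the correlation assumed for each endpoint.

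The cost is one clause and a short statement of method. The systolic pressure claim becomes slightly less favourable, or stays as it is if an unprinted input explains it. The sample size and the other two power statements do not change.
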